Prior to the pandemic, there were calls for increased translational research to inform large scale couples' interventions (12). In the current context, with widespread threat due to far-reaching effects of pandemic stress, this need is even more salient. Introducing novel, brief interventions to address couples' relationships has the potential to mitigate accessibility challenges related to reach and retainment (13). One brief intervention, deemed the "Marriage Hack", targets maladaptive conflict patterns by encouraging couples to reappraise their disagreements from a neutral, third-party perspective (14). This low-resource intervention, which involves three 7-minute writing sessions (for a total of a 21-minute intervention), has been shown to buffer against normative declines in marital quality over time by reducing conflict-related distress. Such an intervention has the potential for widespread scale-up among couples at risk for relationship deterioration. In addition to its brief nature, it also has the advantage of being a fully online intervention, and will therefore reduce access barriers inherent to the pandemic and to couples with young children.

The need for a feasibility study

The overarching goal of this research program is to evaluate the effectiveness of an adapted version of the Marriage Hack intervention with couples of young children using a randomized controlled trial (RCT), and to examine the impact of the intervention on the interparental relationship as well as other family relationships. We propose to adapt this intervention in three ways. First, the original study was conducted with a relatively low-risk sample in terms of risk for couple-related distress. The current study is considered a secondary prevention program in that we are targeting couples at risk for relationship difficulties based on developmental stage

(couples with young children) and context (a global crisis). Second, to optimize reach and retainment, we will adapt the intervention from its original 12-month course to instead run over a 6-week timeframe. The number of writing sessions will remain the same (i.e., three sessions) but will be expedited to one session every two weeks. Finally, the goal of providing this program to couples with young children is to ultimately study the cascading effects on multiple family subsystems and child adjustment. Outcomes beyond the couple relationship were not examined in the original Marriage Hack RCT.

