Best practice for establishing effectiveness through an RCT requires a step-wise approach: (1) a feasibility study to address specific elements of the RCT (e.g., intervention characteristics); (2) a pilot RCT to address barriers and inform parameters of the main RCT; and (3) a main RCT to assess effectiveness (15). The current protocol describes a non-randomised, single-arm feasibility study (step 1 above), with the aim to assess feasibility, identify and rectify problems, and increase the success of a future evaluative RCT.

Objectives

The primary objective of the current study is to assess the feasibility and other methodological components of the Love Together, Parent Together (L2P2) intervention to inform the parameters of a future pilot (step 2 above) and main RCT (step 3 above). L2P2 is a brief conflict reappraisal program for couples with young children designed to support whole family functioning. Primary objectives of the current feasibility study are as follows:

(1) *Recruitment*: Establish partnership with three recruitment sources and provide examine recruitment rates to determine if additional recruitment sources are needed.

(2) *Sample*: Assess whether our recruitment approach and eligibility criteria are appropriate for the intended sample (i.e., participants with mild to moderate levels of couple distress as in a secondary preventive intervention). Relatedly, we are interested in the heterogeneity of the sample obtained through this recruitment approach based on sample demographics including income/education level, racial/ethnic identification, immigration status and history, and sexual orientation/gender identity.

(3) *Program*: Assess program retention, adherence, and uptake rates—that is, the extent to which participants complete the assessment schedule in full, engage in the three writing (intervention) sessions, and report use of conflict-reappraisal strategies in between sessions.

(4) *Measurement*: Conduct a preliminary validation of a primary outcome measure of couple “we-ness” (16) based on a content analysis of writing samples collected during the intervention. This new measure will be used in conjunction with pre-existing self-report measures of perceived partner responsiveness and responsiveness towards one’s partner for a multi-method/multi-informant assessment approach in subsequent pilot/main RCTs.

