Eligibility criteria are as follows: (i) both participants endorse being in a relationship; (ii) partners reside in the same home; (iii) one or more children under the age of 6 living at home; (iv) both participants are over age 18 years; and (v) both members of a couple agree to participate. Exclusion criteria included: (i) no current plans or history of separation or divorce as this is meant to be a secondary preventative intervention for couples experiencing mild-to-moderate but not severe relationship difficulties.

Recruitment sources include: (1) Moms at Work, a community, education and advocacy group supporting women in their careers; (2) Unemployed Help Centre of Windsor Inc., a nonprofit organization assisting the un/underemployed and disadvantaged person during the transition period in the reemployment process; and (3) EarlyOn Child and Family Centres, who offer free, high-quality programs for young families. These recruitment sources were selected to get a range of participants in terms of potential risk factors for relationship problems.

Listsers members from each recruitment source will receive an invitation to participate in research with a direct contact link to the L2P2 study platform via Qualtrics. Participants will go through an eligibility screen, followed by review of a letter of information and informed consent. Once participants have consented, they will be asked for their contact information and that of their partner (if they are the first member of the couple to sign up). The second member of the couple will be contacted directly by the study team via email with an invitation to enroll. Once both members of a couple have enrolled, they will be given couple and participant IDs, and a survey schedule will be set-up and executed. For a schematic diagram of the time schedule of enrolment, intervention, and assessments, see Figure 1.

Intervention

Given that this is a single-arm design, only an intervention group will be described. The intervention sessions will consist of two stages. First, participants will be asked to provide a "summary of a time when you and your romantic partner did not agree in the last two weeks..." focusing on "you and your partner's actions (what you said and did), not about what you were thinking or feeling." Second, participants will be asked to engage in a writing task wherein they

will be instructed to reappraise the conflict they previously reported based on the following prompts (14):

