Mild-moderate risk for relationship distress	% participants scoring 'clinical' (>13) on the Dyadic Adjustment Scale (20) % participants scoring 'high' (>29) on the COVID-19 Family Stressor Scale (21)	< 50% of eligible participants.	
Participant retention	% participants who remain in study until end of post-intervention assessment	> 90% of participants	
Participant adherence	% participants who complete 2/3 intervention sessions	> 90% of participants	
Participant uptake	% participants reporting some use of conflict reappraisal outside of sessions	> 80% of participants	
Acceptability	% of participants reporting at least 'good' on 80 % or more indicators on an Implementation Acceptability Scale assessing attitude, burden, perceived effectiveness, and ethicality (22).	> 80% of participants, (stratified by gender, immigrant status, and racialized groups)	

Primary outcome measure development	Objective assessment of wellness (16) based on content analysis of writing samples. Will include an analysis of first-person plural pronouns (we, us, our, ours), reference to partners' internal states (beliefs, desires, intentions), and positive affective language (23)	Inter-rater reliability (Cronbach's alpha > .80) Internal consistency (Cronbach's alpha > .70) Significant group differences between male and female participants based on t-tests ($p < .05$) Significant correlations ($p < .05$) with indices of convergent validity (i.e., self-reported responsiveness, partner reported perceived partner responsiveness).	

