Secondary objective To Explore: Pre-Post Change in Outcome Measures	
Couples' Relationship Quality: Perceived Relationship Quality Scale (24)
 
Conflict-Related Negativity: two items following fact-based summary: "I was angry at my partner for his/her behavior during this conflict," "My partner's behavior during this conflict was highly upsetting to me" (14).
 
Perceived Partner Responsiveness/Responsiveness Directed Towards Partner: Two eight-item scales will assess participants' perceptions of their partners responsiveness/insensitivity and their own responsiveness/insensitivity towards their partner, respectively (25)
 
Parent-Child Relations, Parenting Practices Scale from the Ontario Child Health Study (26)
 
Parent Mental Health, K10 Psychological Distress Scale (27)
 
Child Emotional and Behavioural Problems, Pediatric Symptom Checklist (Baby, Preschool, and Standard versions) (28)
	Intervention will improve outcomes from baseline to post-intervention surveys	3-level multilevel models, similar to regression analysis but accounting for clustering within data structure

Figures

Figure 1

Schedule of enrolment, intervention, and assessments.

	Study Period					
	Enrolment	Post-Enrolment				
TIMEPOINT	$-t_1$	t_1 Week 0	t_2 Week 1	t_3 Week 3	t_4 Week 5	t_5 Week 6
ENROLMENT:						
Eligibility screen	X					
Informed consent	X					
Contact Information	X					
Allocation						
INTERVENTIONS:						
[Intervention A]			X	X	X	
ASSESSMENTS:						
Demographics, COVID-19 Stress, Relationship Distress		X				
Couples' relationship quality, perceived partner responsiveness, responsiveness to partner, parent mental health, child mental health, parent-child relations		X				X
Conflict-Related Negativity			X	X	X	
Use of Conflict Reappraisal Strategy				X	X	
Acceptability						X

References

2. Kluwer ES. From partnership to parenthood: A review of marital change across the transition to parenthood. *Journal of Family Theory & Review*. 2010;2(2):105-25.

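### The Table 1 distress criterion sets a limit on only one side of the mild-to-moderate target in Objective 2, so a sample with little or no distress would be recorded as a success

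*Protocol*

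**What the plan says.** Objective 2 (Objectives, Sample) asks whether the recruitment approach and eligibility criteria suit "participants with mild to moderate levels of couple distress as in a secondary preventive intervention". The Participants section gives the same target when it explains the exclusion for separation or divorce: the programme is for "couples experiencing mild-to-moderate but not severe relationship difficulties".

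The Table 1 row on mild-moderate risk for relationship distress is the only success criterion for this target. It lists two outcomes: the percentage of "participants scoring 'clinical' (>13) on the" Dyadic Adjustment Scale, and the percentage of "participants scoring 'high' (>29) on the" COVID-19 Family Stressor Scale. One criterion stands against both: "< 50% of eligible participants".

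Elsewhere the protocol describes risk more loosely. The section on the need for a feasibility study speaks of "targeting couples at risk for relationship difficulties based on developmental stage" and of context. Inclusion criterion (iii), "one or more children under the age of 6 living at home", covers the first of these.

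Outcomes and Analysis says that the design (for example recruitment sources or eligibility) will be changed if success indicators are missed. Figure 1 places "Demographics, COVID-19 Stress, Relationship Distress" at the baseline assessment, so both scales are already collected.

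**The concern.** Mild to moderate is a band with a lower and an upper edge. By the row's own labels, the criterion limits only the share above the upper edge. Nothing in the row, the eligibility criteria or the analysis text sets a minimum score, or a minimum share of participants with at least mild distress.

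What is at stake is the answer to a primary objective. If the three listservs mainly bring in contented couples, the study has missed its intended secondary-prevention sample, yet the row would report success. The pilot RCT could then go ahead with the same recruitment and eligibility rules. Couples with little distress at baseline may also have little room to improve on the couple outcomes that the later trials are meant to study.

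**Working it through.** The row states a threshold, not a calculated figure, so there is no plan figure to reproduce. The check is whether the rule can separate the intended sample from an unintended one.

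**Inputs.** The sample is 20 couples, or 40 participants, with data hoped for from 15 couples, or 30 participants (Sample size). The threshold is below 50% (Table 1). The true shares above the cut-offs are not given, so every share below is an assumption. Partners may resemble each other, so I also use an effective n of 20, as if partners always gave the same result.

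**Largest passing count.** x/n < 0.50 gives x ≤ 19 of 40 (47.5%), x ≤ 14 of 30 (46.7%) and x ≤ 9 of 20 (45%). The smallest passing count is 0 in each case.

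**Readings of the row.** (a) Each scale must be below 50%. (b) It is enough that one scale is below 50%. (c) The share of participants above at least one cut-off must be below 50%. (d) The share above both must be below 50%.

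**Sample with no one above a cut-off.** The share is 0/40 = 0% under (a) to (d), and 0% < 50%. The row passes under every reading.

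**Sample with few above a cut-off.** P(pass) = P(X ≤ m), with X binomial(n, p) and m the largest passing count. Take 10% on each scale. Reading (c) is the hardest to pass when no one exceeds both cut-offs, because the combined share is then 10% + 10% = 20%.

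| n | m | P(pass), one scale, p = 0.10 | P(pass), reading (c), p = 0.20 |
|---|---|---|---|
| 40 | 19 | 1.000 | 1.000 |
| 30 | 14 | 1.000 | 0.9998 |
| 20 (effective) | 9 | 1.000 | 0.997 |

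At 10% or less on each scale, the pass probability is therefore above 0.99 under every reading.

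**Where that stops.** At 20% on each scale, reading (c) gives a combined share of 1 − 0.8² = 36% if the scales are independent, or 40% if no one exceeds both. P(pass) is then 0.95 to 0.87 (n = 40), or 0.86 to 0.76 (effective n = 20).

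**Where the readings part.** At 35% on each scale, independent, with n = 40:
- (a) gives 0.964² = 0.93.
- (c) has a combined share of 1 − 0.65² = 57.75% and gives 0.125.
- (d) has a share of 0.35² = 12.25% and gives about 1.00.

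At intermediate shares the verdict depends on the reading. At low shares it does not.

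**The case against.** **Risk is defined by stage and context, not by a score.** A programme meant to prevent decline can reasonably guard only against severe distress, and the child-under-6 criterion secures the developmental stage. This has some force: a ceiling is a coherent safeguard and matches the words about not being severe. It does not remove the point, because Objective 2 names levels of distress and the row measures scores.

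**The consequence is modest.** This is a single-arm feasibility study with descriptive feasibility outcomes. Low scores would be visible in the baseline data, and nothing forbids a design change when a criterion is met. That stands. What is lost is the pre-set trigger, not the information.

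**Each scale below 50% is the natural reading.** It probably is, and table layout may have been lost in the conversion from PDF. A reader might infer that the missing conjunction leaves the whole row undefined; the text does not support going that far. It is a secondary clarification, worth making because the diversity rows in the same table count participants with at least one of two indicators.

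**Stronger claims that do not hold.** A reader might infer that the row passes almost surely even at 20% on each scale, however the scales are joined. It does not if participants above either cut-off are counted (0.76 to 0.95 in the cases above). A reader might also infer that the >13 cut-off points the wrong way. The protocol gives no scoring key, so its direction can only be queried.

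**Conclusion.** The concern holds in a limited form. Under the document's own labels, the criterion has a ceiling and no floor. It can show that the sample is not mostly severe, but it cannot show that the sample reaches mild distress, which is half of what Objective 2 asks. With none above the cut-offs it passes with certainty. With true shares of 10% or less on each scale it passes with probability above 0.99, whether partners are independent or fully alike.

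The zero-count result needs no assumption beyond the labels. The probabilities rest on assumed shares and a binomial model. If a score above 13 meant better adjustment, the Dyadic Adjustment Scale part of the row would act as a lower limit on distress and its severe side would be open. That scale would still be limited on one side only.

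The change should be made before data are seen. No treatment or efficacy conclusion depends on this row, and descriptive reporting would soften the harm.

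**What to change.** Before any data are seen:

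1. Check the direction of the >13 cut-off against the Dyadic Adjustment Scale scoring key.
2. Make the row two-sided by adding a limit, set by the sponsor, on whichever side is open. If a score above 13 means more distress, keep the present ceiling and add a minimum share of baseline completers in a mild-to-moderate band. If it means less, the limit to add is on the severe side.
3. In the same edit, state whether the 50% applies to each scale separately or to participants above either cut-off.

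The cost is one Table 1 row and no new data, since both scales are collected at baseline. The downside is that the criterion becomes harder to meet and can be missed by chance. As an illustration, assume a minimum of more than 30% in the band and a true share of 40%. With n = 40 at least 13 participants are needed, and P(X ≤ 12) = 0.13. With an effective n of 20 at least 7 are needed, and P(X ≤ 6) = 0.25. The sponsor should choose the minimum with that risk in view.

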Several steps will be taken to improve adherence to intervention protocols. The current feasibility study will be conducted online to reduce barriers to participation. The survey and intervention sessions will be made available for mobile and/or computer users to enhance access and promote adherence. Remuneration of participants will occur as the study progresses (i.e., after each session) via email in the form of a choice of gift card. Specifically, each participant will receive \$5.00 for the baseline survey, \$10.00 for each of the three intervention sessions, and \$5.00 for the post-intervention survey (\$40.00 per participant for full participation). Reminders of study timelines and survey/intervention session expiry dates will be provided by email.

Outcomes and Analysis

Table 1 presents all study objectives with associated outcomes, and criteria for success of feasibility, hypothesis for secondary outcomes, and methods of analyses, when applicable. Feasibility outcomes will be reported descriptively using descriptive statistics, means (standard deviations) and frequencies/percentages. Analyses for pre-post change and validation of an objective primary outcome measure are described in Table 1. If success indicators are not met, we will make changes to study design accordingly (e.g., expand recruitment sources, adjust eligibility criteria, adapt intervention schedule and/or compensation). Analyses will include all

participants who complete baseline assessments, using Bayes estimation, which is more robust with small sample sizes.

Sample size:

We chose the sample size of 20 couples (with expected attrition), with the goal of having data for 15 couples (N = 30). This will allow us to examine rates of recruitment over several weeks, appropriateness of eligibility criteria and reasons for exclusion, diversity of sample, retention, adherence, and uptake, as well as preliminary analyses examining pre-post change and the validity of a new primary outcome measure.

The current protocol does not include stopping or discontinuing guidelines.

Data Management

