The current feasibility study is funded by York University, Faculty of Health, with generic funds provided to the Principal Investigator ([name]). Funders have no role in the project, including in study design, collection, management, analysis, and interpretation of data, writing of the report, and/or decision to submit the report for publication.

Authors' contributions

HP: Study conceptualization and design, oversight of the development of the study protocol, survey development, recruitment, and data collection, initial draft of the manuscript.

AM: Study conceptualization and design, substantive revision of the manuscript.

VB: Development of the study protocol, survey development, and substantive contributions to the drafting of the manuscript.

LT: Study conceptualization and design, substantive revision of the manuscript.

MW: Study conceptualization and design, substantive revision of the manuscript.

All authors have approved the submitted version of the manuscript and have agreed to be personally accountable for their contributions.

Acknowledgements

Thank you to Drs. [name], [name], and [name], for their consultation on study design. In addition, thank you to [name] for critically reviewing the study protocol and survey development, and to [name] for her coordination of the project.

Authors' information (optional)

Not applicable.

Tables

Table 1

Primary Objectives To Determine:	Outcome	Criteria for 'success' of feasibility/hypothesis	Method of analysis
Recruitment	Number of participants Accessed (I.e., initiate registration) per week, stratified by recruitment source	10 couples per week over the course of 4 weeks who access our registration site	Descriptive statistics
	Number of participants Enrolled per week, stratified by recruitment source	5 couples per week over the course of 4 weeks who enroll in the study	
Eligibility criteria	% interested participants that meet Inclusion Criteria (with reasons for exclusion)	< 50% of participants are excluded for any one criterion.	
Sample diversity	% participants income <= regional median, <= high school degree	> 30% of our sample has 1+ indicator.	
Sample diversity (race/ethnicity/immigration)	% participants racialized, immigrant	> 30% of our sample has 1+ indicator.	
Sample diversity (sexual orientation/gender)	% participants non-heterosexual, gender non-conforming	> 30% of our sample has 1+ indicator.	

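### A significant male/female difference is a success criterion for the we-ness measure, but the protocol gives no direction, size or reason for it, and a sound measure would usually miss it at this sample size

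*Protocol*

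**What the plan says.** The Measurement objective is to "Conduct a preliminary validation of a primary outcome measure of couple" we-ness from the writing samples, for use beside existing self-report responsiveness scales in the later pilot and main trials. It does not mention sex or gender.

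The Outcomes and Analysis section states "Analyses for pre-post change and validation of an objective primary outcome measure are described in Table 1". In Table 1 the relevant column is headed "Criteria for 'success' of feasibility/hypothesis", and the row for primary outcome measure development has four entries in it:

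- inter-rater alpha above .80;
- internal-consistency alpha above .70;
- "Significant group differences between male and female participants based on t-tests" (p < .05);
- correlations, also required to reach p < .05, with self-rated responsiveness and with responsiveness as the partner perceives it.

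The Sample size section plans 20 couples "with the goal of having data for 15 couples (N = 30"). Both partners take part (Participants section). The pre-post row of Table 1 names "3-level multilevel models, similar to regression analysis but accounting for clustering within data structure"; the we-ness row says nothing about couples. The Outcomes and Analysis section adds that unmet success indicators will lead to changes in study design.

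**The concern.** A success criterion should test a property that the measure must have if it is valid. Reliability and correlation with responsiveness scales do that. A sex difference does so only if theory says that men and women differ in we-ness, and in which direction. The protocol states neither, so a difference either way counts as success and no difference counts as a shortfall.

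Two things follow. A reliable measure with good convergent validity would be reported as short of a criterion if men and women are alike on the construct. And if a moderate difference is real, about 15 couples are too few to show it dependably, so a miss says little about the measure. Validation of we-ness is a primary objective, and unmet indicators feed into redesign, so a miss could prompt changes to an instrument that works.

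**Working it through.** **The plan's own figures.** 15 couples × 2 partners = 30 individuals, as stated. The protocol gives no power, effect size or standard deviation for the sex test, so there is no power figure to reproduce.

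**Inputs.** From the Protocol: p < .05; 15 couples with data, 20 enrolled. Assumed, because the Protocol is silent: two-sided testing, one we-ness score per person, all couples male/female, equal SDs, a true standardised difference d = 0.5 for illustration, and partner correlation ρ of 0, .3 or .5.

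**No true sex difference.** A single valid two-sided test at .05 is significant 5% of the time at any sample size, whatever the reliability or convergent validity of the measure.

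**True d = 0.5, paired t-test.** The effect on the within-couple difference is dz = d / √(2(1 − ρ)), and the noncentrality is dz × √n with n − 1 degrees of freedom. With n = 15 the critical t is 2.145.

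| ρ | dz | noncentrality, n = 15 | chance of meeting criterion, n = 15 | same, n = 20 |
|---|---|---|---|---|
| 0 | 0.354 | 1.369 | 25% | 32% |
| .3 | 0.423 | 1.637 | 33% | 43% |
| .5 | 0.500 | 1.936 | 44% | 56% |

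Solving the same formula for 80% power with 15 couples gives d = 1.10 / 0.92 / 0.78 at ρ = 0 / .3 / .5.

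**True d = 0.5, unpaired t-test on the same paired data.** By simulation (400,000 runs per setting), the criterion is met 26% / 23% / 20% of the time with 15 couples and 34% / 31% / 29% with 20. Positive partner correlation makes this test conservative: with no true difference and 15 couples it is significant in 2.1% of runs at ρ = .3 and 0.8% at ρ = .5.

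**What an interval would show.** The 95% half-width for the paired difference, in SD units, is t(.975, n − 1) × √(2(1 − ρ)/n). With n = 15 and ρ = 0 this is 2.145 × √(2/15) = 0.78; at ρ = .3 and .5 it is 0.66 and 0.55.

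**Convergent correlations pooled over individuals.** With a true correlation of zero, and partner correlation .3 or .5 on both variables, a Pearson test on 30 individuals is significant in about 6% or 8% of runs against a nominal 5%. The excess is modest.

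**The case against.** The strongest defence is that comparing groups expected to differ is an ordinary validation step (known-groups validity), and that the reason may lie in the sources cited in the row, which were not available. That stands as far as it goes: the criterion cannot be called baseless, only unexplained. A known-groups test still needs a stated direction, and the low pass rate at 15 couples remains even if the expectation is right.

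Several stronger readings are tempting, and the document does not support them.

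- *The plan specifies an unpaired test that ignores couples.* It does not say which t-test is meant, and that choice can properly sit in a statistical analysis plan. The sex criterion itself is fixed in the protocol.
- *A measure without a sex difference can never pass more than 5% of the time.* This holds for a single valid test. An unpaired test with negative partner correlation (ρ = −.3) is significant in about 8.4% of runs. If three language components were each tested and one sufficed, the chance rate could approach 1 − 0.95³ = 14%, assuming independence. A sound measure would still usually miss.
- *Missing the criterion rejects the measure.* The protocol does not say how the four entries combine, calls the validation preliminary, and plans to use we-ness beside existing scales.
- *The p-values contradict the stated approach, "using Bayes estimation, which is more robust with small sample sizes".* That is a general sentence beside a specific table row: loose wording, not a clear conflict.

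**Conclusion.** The point holds for the sex criterion. Table 1 counts a significant male/female difference as success without a stated direction, size or reason. Success then depends on whether the sexes happen to differ and on how many couples enrol, more than on the quality of the measure. With no true difference, a single valid test meets the criterion 5% of the time. With an assumed d of 0.5 and 15 couples, the figure is 25% to 44% paired and 20% to 26% unpaired, for partner correlations of 0 to .5. The effect size and partner correlations are assumptions, but only a large difference (about 0.8 to 1.1 SD, paired) would be found with 80% power.

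The handling of couples in the correlations is a lesser point of modest size. The change is worth making because it alters which result counts as success. It does not affect participants or the other feasibility criteria.

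**What to change.** Remove the male/female difference from the success criteria in this row and report it descriptively, with a 95% interval that allows for couples. If theory predicts a difference, state its direction and reason as a hypothesis, and do not make significance at this sample size the pass mark.

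Estimate the convergent correlations with a method that allows for couples, such as a couple-level bootstrap or a couple random effect, and report them with intervals.

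The method for the sex comparison should also accommodate same-sex couples and gender non-conforming participants. Table 1 sets a target above 30% for participants who are non-heterosexual or gender non-conforming. A plain paired male/female test would leave out same-sex couples, and a two-group contrast would leave out those who are neither.

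The cost is the wording of one table row, on the same data. The downside is that a yes/no significance claim on the sex difference is lost.
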